12.0 MATERIAL AND METHODS

12.1 Human Resources for The Preparation of the Study

- Three general Practitioners
- One odontologist
- Two nurses
- One computer technician
- One social worker
- Four nutritionists

12.2 Material Resources for the Preparation of the Study

Educational program by grade level (Appendix I)

Session	Theme
I. Water goes through my body	Importance of water for health
II. Am I drinking enough water?	The color of urine as an indicator of the volume of water consumed
III. I love water "Matarile, ríle, ron"	Ecology and water care
IV. Together we take care of our health	Commitment to water consumption

Educational material (Appendix I)

- *Teacher by grade level*

- Hand puppet
- Handbook for each grade level

- *Students by grade level*

CD

- Corresponding audio-story
- Exhort "1, 2, 3... I prefer to drink more water "
- Water Song
- Cheer for healthy urine

Poster

- Individual conclusions poster

- Group conclusions poster
- Healthy urine poster "Watch the color and have control"

Games

- Group game with dice and tokens (Fountains and Waterfalls, Waterthon Water-challenge)

Others

- Wristband with the slogan "I Prefer Plain Water"
- Mobile app for personal, group, and family commitments

- Family

- Diptych

Method

12.3 Site and Participants

A community intervention trial will be conducted within the Coyoacán Delegation located in southern Mexico City. The four IG schools included in the previous study will be invited to participate. First graders will be recruited during the 2017-2018 school year. A medical examination (Appendix II) will be conducted for all participants within the school facilities as a direct benefit to the community. Documents regarding the original medical examination will be provided to the parents to be turned in at the school as requested, and a copy of the children's document will be obtained for parents who consent to their participation in the study. All healthy children whose parents sign a privacy notice (Appendix IV) and complete the 3-day baseline consumption of beverages questionnaire will be included (Appendix V) after reading an information letter (Appendix III), being given the opportunity to ask questions, clarify doubts, and agree to participate in the study. The parents will express their acceptance via verbal informed consent. The verbal consent process will be documented in the file of each participant.

12.4 Intervention

At all participating schools, the principal investigator will conduct an approximately 1-hour briefing for parents to 1) explain the study's operational generalities and answer all questions and 2) provide instructions for completing the beverage consumption survey. Subsequently, the 3-day baseline record of beverage consumption will be collected.

At the beginning of the school year, first grade teachers will be trained by a nutritionist (one per school) to dispense the educational sessions (Appendix VI, VII, VIII), and the manual and materials for both teachers and students will be delivered.

The students will receive four educational sessions of approximately 1 hour. These sessions will be given every 2 weeks, and some will be supervised by a nutritionist.

The four schools will be assigned to one of the following three groups based on school enrollment and the interest of the teachers in participating:

Students in Group I will receive the education strategy only during the first grade; students in Group II will receive the educational strategy during first and second grades; and students in Group III will receive the educational strategy during first, second, and third grades.

	1st grade	2nd grade	3rd grade
Group I	X		
Group II	X	X	
Group III	X	X	X

With the delivery of the first educational session, free access to water will be initiated through Welltek water dispensers, model WT-POU-300 A (approved and certified by Cofepris and the National Institute of Physical Educational Infrastructure; INIFED), installed inside the classrooms. Children will also receive a reusable 600-mL bottle (twice) so that they may consume water throughout the day. The availability of water will be guaranteed during four school cycles.

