7.1 Primary Objective

This study seeks to compare the percentage of water consumed among early elementary school children receiving one, two, or three interventions of the educational strategy "I Prefer Plain Water" at a 1-year follow-up evaluation.

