9.0 STUDY DESIGN

Experimental, analytical, longitudinal, and prospective designs will be employed. The assignment will be conducted by each school.

Community Intervention Test

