12.5 Evaluation Process

In September 2017, the medical examination of the students and the process of inclusion will be performed; instructions will be sent to parents, and teacher training will be conducted. During October 2017, the baseline record regarding the consumption of beverages will be collected (Time 1). The educational sessions will be given from November 2017 to January 2018. A second record (Time 2) will be obtained at the end of the interventions in each group (end of June), and a third record (Time 3) will be obtained from each group 1 year after completing the interventions (end of June).

Baseline		End of 1st grade	End of 2nd grade	End of 3rd grade	End of 4th grade
Group I	X	X	X		
Group II	X	X		X	
Group III	X	X			X

 Evaluation 1 year after completing the number of interventions associated with each group

In addition to measurements at baseline and at each evaluation time, body weight will be measured, and lean mass, fat free mass, fat percentage, total body water, and BMI will be analyzed using a body composition analyzer via electrical bioimpedance (TANITA TBF-310 GS). Height will be measured using a portable stadiometer (dry mark, model 213, Hambur Germany). Participants will be measured in light clothing (T-shirt and sport shorts) and without shoes. A nutritionist will be calibrated to perform the measurements. BMI will be classified using the WHO values standardized by age and gender.

The following table summarizes the procedures to be performed throughout the trial.

Procedure	Sep 2017	Jun 2018	Sep 2018	Jun 2019	Sep 2019	Jun 2020	Sep 2020	Jun 2021
School medical examination	X							
Weight, size, and body composition measurements	X	X		X		X		X
Instructions for completing the daily beverage record	X	X		X		X		X
Teacher training	X		X		X			
Daily beverage record	X	X		X		X		X
Group I intervention	X							
Group II Intervention	X							
Group III Intervention	X							

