13.0 SAMPLE SIZE

Considering the results of the previous study where a mean difference of 80.74 mL was found with regard to water consumption with an SD of 399 mL as well as considering an α of 0.05 and a β of 0.1, we used the following formula to calculate a significant difference in means

$$n = [(Z_{1-\alpha} + Z_{1-\beta})^2 * s^2] / d^2$$
$$[(1.96 + 1.28)^2 * 399^2] / 80.74^2 = 256.36$$

N = 257 children

The sample should include 329 first graders (allowing for a 28% loss margin) who will attend the 2017-2018 school year. This sample represents all of the four intervention schools that participated in the previous study.

2016-2017 school enrollment of the intervention schools participating in the previous study

School	Health Center	First grade	Total	Second grade	Total	Third grade	Total	Total school enrollment
Ramón Durand	Ajusco	32 32	64	31 32	63	26 27	53	341
Xitle	Ajusco	27 29 25	81	28 27 29	84	31 30 29	90	529
Guillén de Lampart	Santa Úrsula	28 26 27	81	31 32 30	93	27 27	54	475
Tlamatini	Santa Úrsula	34 35 34	103	36 37 36	101	33 33 33	99	600
			329		278		243	1,604

	Group I	Xitle	81
	Group II	Guillén de Lampart	81
	Group III	Ramón Durand Tlamatini	167

Based on the school enrollment of the current school year (2016-2017), schools with the same number of first graders will be assigned to Groups I and II. For Group III, the schools with the highest and lowest enrollments will be added.

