15.0 STATISTICAL ANALYSIS

The analysis will be performed using the IBM SPSS version 22.0, and non-parametric statistics will be used.

Baseline measurement of beverage consumption (Time 1). The basal consumption of the different beverage categories will be summarized using medians, minimums, and maximums. We will apply the Kruskal-Wallis test (K of independent samples) to compare the differences in baseline beverage consumption among the three groups.

Baseline measurement and at the end of the interventions (Times 1 and 3). The percentage of water consumed at baseline will be compared with that 1 year after finishing the intervention for each group using the Wilcoxon test.

Comparison among the three groups. The percentage of water consumed will be compared among the three groups 1 year after the intervention is completed using Friedman's test of related samples.

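### Number of interventions is aliased with school, and at the final record with grade and calendar year, so the primary comparison describes four schools and cannot test the number of interventions

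*Combined protocol and SAP*

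**What the plan says.** The primary objective (Section 7.1) is to "compare the percentage of water consumed among early elementary school children receiving one, two, or three interventions" at a 1-year follow-up. Section 8.0 predicts the highest percentage in the group given all three. Section 3.0 says the result should help decide how many interventions children need, as a basis for public health policy.

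On allocation, Section 9.0 says "The assignment will be conducted by each school". Section 12.4 has the four schools "assigned to one of the following three groups based on school enrollment and the interest of the teachers in participating". Section 13 mentions enrolment only: "schools with the same number of first graders will be assigned to Groups I and II" and "For Group III, the schools with the highest and lowest enrollments will be added". Its table gives 81 first graders in Group I (one school), 81 in Group II (one school) and 64 + 103 = 167 in Group III (two schools). Random assignment appears only in the account of the previous study (Section 4.5.2).

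On timing, the Section 12.5 text says "A second record (Time 2) will be obtained at the end of the interventions in each group". The table below it instead shows an end-of-1st-grade record for all three groups, and then one described as "Evaluation 1 year after completing the number of interventions associated with each group".

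On analysis, Section 15 has three parts: a Kruskal-Wallis test of baseline consumption among the groups; a Wilcoxon test of baseline against 1 year within each group; and the between-group comparison, in which percentage of water "will be compared among the three groups 1 year after the intervention is completed using" Friedman's test. No school term, ICC or baseline covariate is given for that last comparison.

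**The concern.** When each group is one or two whole schools, any difference between schools is also a difference between groups. Teaching, families, the neighbourhood and how carefully parents keep the journal can all differ by school. A child-level test takes its error only from variation between children, so an ordinary difference between two schools can come out as a significant effect of more interventions. Since Section 3.0 ties the result to policy, it will be read beyond these four schools.

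Two features add to this. The final record is taken at a different grade and in a different calendar year in each group. And Section 12.4 lets teacher interest bear on allocation, although teachers deliver the sessions and Section 4.5.1 treats their example as central to the strategy.

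**Working it through.** **The plan's own figure.** Section 13: (1.96 + 1.28)² × 399² / 80.74² = 256.36, so 257; 257 × 1.28 = 328.96, so 329. Both reproduce. Neither contains a school component.

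**Can group and school be separated?** With four schools and three groups, a design matrix holding group and school has rank 4, the same as school alone. The group effect is fully aliased with school. If school is treated as random instead, 4 − 3 = 1 between-school degree of freedom remains (two-sided 5% critical t of 12.71), and it comes only from the two Group III schools. Groups I and II, with one school each, contribute none.

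**Timing of the final record.** First grade ends in June 2018. One year after the last intervention is the end of 2nd grade, June 2019 (Group I); the end of 3rd grade, June 2020 (Group II); and the end of 4th grade, June 2021 (Group III). Grade and year move in step with group.

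**Type I error if the test is read beyond these schools.** The documents give no ICC, so the values below are assumptions. Children per school are enrolment less the plan's 28% loss: 81 × 0.72 = 58 (Groups I and II), 64 × 0.72 = 46 and 103 × 0.72 = 74 (Group III). For I against II, the design effect is DE = 1 + (58 − 1) × ICC and the type I error is 2 × [1 − Φ(1.96/√DE)]. The three-group column is a simulation (40,000 runs, normal data with random school effects). It uses Kruskal-Wallis as the child-level test for independent groups; that Section 15 names Friedman's test is a separate matter and carries no weight here.

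| Assumed ICC | DE | I vs II | Three groups |
|---|---|---|---|
| 0.001 | 1.057 | 5.7% | 5.7% |
| 0.005 | 1.285 | 8% | 9% |
| 0.01 | 1.57 | 12% | 14% |
| 0.02 | 2.14 | 18% | 24% |
| 0.05 | 3.85 | 32% | 46% |

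Over ICC 0.005 to 0.05, I against II gives 7% to 25% with 40 children per school and 10% to 38% with 81. If error is taken strictly from within-school variation, the variance ratio is 1 + n × ICC/(1 − ICC). At n = 58 and ICC 0.05 this gives 33.0% rather than 31.8%, so the table is slightly low.

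**Precision with unlimited children.** Only school variation is left. In SDs of the outcome, the 95% half-width is 1.96 × √(2 × ICC) for I against II (one school each) and 1.96 × √(1.5 × ICC) for III against I (two schools against one, equally weighted).

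| Assumed ICC | I vs II | III vs I |
|---|---|---|
| 0.005 | 0.20 | 0.17 |
| 0.01 | 0.28 | 0.24 |
| 0.02 | 0.39 | 0.34 |
| 0.05 | 0.62 | 0.54 |

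**On the plan's mL scale.** If 399 mL is taken as the total SD, ICC 0.02 gives a chance difference between two schools with SD 399 × √(2 × 0.02) = 79.8 mL, about the size of the 80.74 mL planning effect. The primary variable is a percentage, so this is only a guide to scale.

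**The case against.** **Teacher interest may matter little.** A reader might infer that keener schools were steered into Group III. The documents do not show this. If the Section 13 enrolment rule binds, Group III is fixed as the largest and smallest schools, and interest can decide only which 81-child school is Group I and which is Group II. The phrase may also mean no more than willingness to take part. This stands: selection by interest is possible, not shown. The aliasing with school holds on any reading.

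**Baseline is used.** Section 15 compares the groups at baseline and tests change within each group, and Section 14 defines effectiveness as an increase from baseline. That is true, but none of these adjusts the comparison among groups, and adjustment would not remove the aliasing in any case.

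**The ICC is assumed and could be very small.** This also stands. The outcome is a journal kept by parents at home, and at 0.001 there is almost no inflation. The practical size of the problem is therefore uncertain. The aliasing, and the confounding with grade and year, do not depend on the ICC.

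**The different grades follow from the chosen endpoint.** Section 4.5.2 gives a reason for assessing one year after the intervention. That is a legitimate target, but it still leaves grade and year inseparable from group.

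**Add a school term, or randomise the four schools.** A fixed school term is aliased with group. Drawing lots would remove selection by interest but would still leave one, one and two schools. Neither turns the comparison into a test of the number of interventions.

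**Conclusion.** The point holds. Whole schools are allocated 1, 1 and 2 without randomisation, and the between-group comparison has no school term or baseline covariate. The Section 7.1 comparison and the Section 8.0 hypothesis therefore cannot be tested as an effect of the number of interventions; more children per school would not change that. This rests on the documents alone.

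The size rests on the assumed ICC, normal data and 28% loss: type I error of about 8% to 32% for I against II and 9% to 46% for three groups over ICC 0.005 to 0.05, falling to about 5.7% at 0.001. These rates apply only when the result is generalised beyond the four schools. For a statement about these schools alone, ordinary child-level intervals are valid, but the difference they describe still mixes school, grade, year and number of interventions.

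A reader might go further and conclude that the comparison is biased in favour of Group III. The documents support no direction or size of bias. Nor does the plan claim a confirmatory test in those words; the difficulty is that its hypothesis and policy purpose invite that reading.

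**What to change.** 1. **Section 15.** Replace the unadjusted between-group test with baseline-adjusted estimates of percentage of water for each of the four schools, arranged by group. Show the end-of-1st-grade values beside them, when each group has had one intervention. This is a display; a non-significant difference there should not be taken to show that the schools are comparable. Reconcile the text and table of Section 12.5 so that this record is clearly collected in all groups.

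2. **Sections 7.1, 8.0 and 15.** State that the between-group comparison describes these four schools, is confounded with school, grade and calendar year, and is not a confirmatory test of the number of interventions. If intervals are meant to generalise, add a sensitivity range for school ICC 0.005 to 0.05, computed from the numbers achieved.

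3. **Sections 12.4 and 13.** Reconcile these into one allocation rule in which teacher interest does not decide the number of interventions. Drawing lots among the enrolment blocks (81; 81; 64 + 103) is optional. It requires every school to accept any group, a refusal by either single-school block would leave a group empty, and it does not separate school from number of interventions.

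The cost is new wording and no measurement beyond the Section 12.5 table. The price is wider intervals if generalising and no confirmatory p-value for the primary comparison. A confirmatory test would need more schools per group, which is a larger trial and is not asked for here.

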12.5 Evaluation Process

In September 2017, the medical examination of the students and the process of inclusion will be performed; instructions will be sent to parents, and teacher training will be conducted. During October 2017, the baseline record regarding the consumption of beverages will be collected (Time 1). The educational sessions will be given from November 2017 to January 2018. A second record (Time 2) will be obtained at the end of the interventions in each group (end of June), and a third record (Time 3) will be obtained from each group 1 year after completing the interventions (end of June).

Baseline		End of 1st grade	End of 2nd grade	End of 3rd grade	End of 4th grade
Group I	X	X	X		
Group II	X	X		X	
Group III	X	X			X

 Evaluation 1 year after completing the number of interventions associated with each group

In addition to measurements at baseline and at each evaluation time, body weight will be measured, and lean mass, fat free mass, fat percentage, total body water, and BMI will be analyzed using a body composition analyzer via electrical bioimpedance (TANITA TBF-310 GS). Height will be measured using a portable stadiometer (dry mark, model 213, Hambur Germany). Participants will be measured in light clothing (T-shirt and sport shorts) and without shoes. A nutritionist will be calibrated to perform the measurements. BMI will be classified using the WHO values standardized by age and gender.

The following table summarizes the procedures to be performed throughout the trial.

Procedure	Sep 2017	Jun 2018	Sep 2018	Jun 2019	Sep 2019	Jun 2020	Sep 2020	Jun 2021
School medical examination	X							
Weight, size, and body composition measurements	X	X		X		X		X
Instructions for completing the daily beverage record	X	X		X		X		X
Teacher training	X		X		X			
Daily beverage record	X	X		X		X		X
Group I intervention	X							
Group II Intervention	X							
Group III Intervention	X							

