4.5.1 Pedagogical support of the educational strategy "I Prefer Plain Water"

The educational strategy "I Prefer Plain Water" was designed based on the postulates of three theories of knowledge that have proved useful in behavior modification and the development of life skills, which together lead children to build a permanent foundation to acquire healthy lifestyles.

The first theory is *social cognitive* and exposes individuals to the acquisition of knowledge, rules, skills, habits, and strategies by observing others and socializing and interacting with the environment. Here, the individual modifies his or her behavior by observation and modeling. In turn, the individual influences other members of the social environment.

Albert Bandura, lead proponent of this position, argued that it is necessary to identify the influences that explain why and how a behavior is conducted to modify it. These influences are known as "determinants" or "mediators" of behavior.

This strategy uses five mediators to modify behaviors:

Expected results. The strategy enables students to easily visualize the benefits (expected results) that will be gained by simply increasing water consumption through characters in vignettes, posters, and an exchange of knowledge and experiences within the group.

Behavioral capacity. In each educational session, children set a feasible water-consumption goal, monitor themselves for the prescribed time, and acknowledge their progress. They are recognized for their effort, thereby demonstrating that they can adopt the desired behavior (behavioral change of an increase in water consumption).

Modeling and learning by observation. This strategy's core point is the example of the teacher modeling water consumption at different times. Moreover, children can be peer models for each another.

Self-efficacy. This strategy offers students frequent opportunities to drink water and prove to themselves that they are able to change their habits with regard to the expected behavior. Self-efficacy represents a way for them to evaluate whether they are properly hydrated through observing the color of their urine.

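### Teacher training precedes the October 2017 baseline record, and strategy materials are delivered with it, so Time 1 is not protected from early exposure

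*Combined protocol and SAP*

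**What the plan says.** Section 12.5 gives the 2017 sequence. In September come the medical examination, inclusion and the instructions to parents, and in the same sentence the training, followed by the baseline record: "teacher training will be conducted. During October 2017, the baseline record regarding the consumption of beverages will be collected (Time 1"). After that, "The educational sessions will be given from November 2017 to January 2018".

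Section 12.4 describes the same training without naming a month: "At the beginning of the school year, first grade teachers will be trained by a nutritionist (one per school) to dispense the educational sessions". The sentence goes on "and the manual and materials for both teachers and students will be delivered". Free water comes later: "With the delivery of the first educational session, free access to water will be initiated through Welltek water dispensers".

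Section 4.5.1 lists the mediators through which the strategy is meant to change behaviour. On modelling, it says that the strategy's "core point is the example of the teacher modeling water consumption at different times".

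Three planned analyses use Time 1. Section 15 compares the groups at baseline with the Kruskal-Wallis test, and compares each group's percentage of water at baseline with its value a year after its last intervention by the Wilcoxon test. Section 14 defines effectiveness as a yes/no increase in that percentage over baseline, with no minimum increase. The remaining analysis in Section 15, among the three groups, uses only the later percentage.

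**The concern.** A baseline should be taken before any part of the intervention can act. Here the teachers, who are the agents of the strategy, are trained first. On the most natural reading of Section 12.4, they also have the manual and the classroom materials in hand when the parents fill in the baseline journals. Section 12.2 shows what those materials include: posters on urine colour, audio stories and songs, a slogan wristband and a mobile app.

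A teacher who has just been trained to set an example by drinking water may begin at once, and the protocol does not ask otherwise. Any rise in the children's share of water before or during the October record would then be counted as their starting level. Once the record has been taken, the true starting level cannot be recovered.

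**Working it through.** The plan states no figure that bears on this point, and the sample size in Section 13 does not depend on the order of training and baseline. The check sets the sections side by side and follows an early effect through each analysis.

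**Step 1: the order of events in 2017.**

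| Event | When | Where stated |
|---|---|---|
| Teacher training | September | 12.5 |
| Delivery of materials | Start of the school year, same sentence as training | 12.4 (September is inferred) |
| Baseline journal, Time 1 | October | 12.5 |
| First session | From November | 12.5 |
| Dispensers | With the first session | 12.4 |
| Teacher modelling | No start date | 4.5.1 |

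The months alone allow a gap between training and a journal of anything from 1 day (30 September to 1 October) to 60 days (1 September to 31 October: 29 days left in September plus 31). The documents do not narrow this.

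The procedures table in 12.5 does not settle the order. Its September 2017 column holds the training, the beverage record and all three group interventions together.

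**Step 2: is there a route to the children before November?** The sessions and the dispensers offer none, because both come after Time 1. Teacher modelling does offer one: Section 4.5.1 describes it as happening at different times and does not confine it to sessions. The materials are a second possible route, if teachers use or hand out any of them on receipt. No section forbids either before Time 1 closes, and no section says that either happens.

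**Step 3: what an early effect would do.** For one child, let P0 be the percentage of water before any exposure, e (zero or more) the early rise already present in October, and P3 the percentage at Time 3. Assume that a start a few weeks earlier leaves P3 unchanged. The recorded baseline is then P1 = P0 + e.

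- Within-group change: P3 − P1 = (P3 − P0) − e. The measured change is smaller than the true one by e, so a true increase larger than e is biased toward zero.
- Yes/no effectiveness: a child counts as a success if P3 > P1. A child with P0 < P3 ≤ P0 + e moves from yes to no. As Section 14 sets no minimum increase, even a small e can change the classification of children near the boundary.
- Baseline Kruskal-Wallis test: if e is the same everywhere, the groups shift together. If e differs by school, the groups can differ at P1 even when they do not differ at P0.
- Among-group comparison at Time 3: this uses P3 alone, so e does not enter.

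**Step 4: could e differ by group?** All three groups follow the same first-grade schedule, which argues for a shared effect. However, Section 12.4 assigns schools partly on how interested their teachers are, and Section 13 gives Groups I and II one school each. One school's early start would not be averaged out within its group. A difference is therefore possible, but the documents do not show one.

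**The case against.** The strongest reply is that the protocol describes a sensible order: prepare the teachers, take the baseline, then start. Section 4.5 says that the strategy consists of four sessions, and Section 14 counts an intervention by the student's receipt of it. Section 12.4 gives the purpose of training as delivering those sessions. On that view, training and handing over materials are preparation, and Time 1 comes before the intervention. This stands as far as it goes: nothing dated and aimed at the children comes before October.

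A reader might go further than the evidence and conclude that part of the intervention starts before Time 1 and that the baseline is contaminated. The documents do not support this. They describe no early modelling and no early use of materials, and the September date for the materials rests on a shared sentence. Nor does the shared September 2017 column in the procedures table show intervention before baseline: the text gives October and November, and the columns look like coarse period labels.

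A reader might also infer that every effectiveness result is at risk. That is too broad. The primary objective in 7.1 and the hypothesis in 8.0 concern the percentage of water among the groups at follow-up, and Section 15 makes that comparison without subtracting baseline.

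Finally, any shared effect would be conservative, and some teachers may already know the strategy, because all four schools were intervention schools in the previous study. Both points are fair. What the reply leaves unanswered is that modelling has no start date and no instruction to wait, although the protocol treats it as central.

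**Conclusion.** The point holds as an unprotected baseline. It is not a demonstrated bias. That training precedes Time 1 is certain from 12.5. That the materials arrive with it is a reasonable reading of 12.4. That teachers would act early is a possibility only.

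If they did, the within-group Wilcoxon comparison and the yes/no effectiveness variable would understate the change, and an uneven start across schools could enter the baseline Kruskal-Wallis comparison. The among-group comparison at Time 3, as written, is not directly affected.

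The size of any early effect is unknown. The documents give nothing from which to estimate it, and a volume derived from an assumed fraction of the previous study's result would be invention.

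The conclusion on direction rests on three assumptions: early modelling raises the share of water rather than lowering it, a slightly earlier start does not alter the Time 3 level, and a change at school shows up in a journal that parents complete at home. The change is worth making because it costs little and a lost baseline cannot be recovered.

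**What to change.** In 12.4 and 12.5, schedule the 2017 first-grade teacher training, and the delivery of all teacher and student materials, after each school's last baseline journal has been collected and before that school's first November session. Add one sentence stating that no strategy material is used and no teacher modelling begins until Time 1 is closed at that school. In the procedures table, split the September 2017 column so that it shows baseline record, training and first session in that order and agrees with the text.

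The cost is a shift of a few weeks in the 2017 calendar, with no added staff, visits or children. There are two downsides. The interval between training and the first session becomes shorter. The change also cannot remove any familiarity that teachers keep from the previous study in the same schools, so it reduces the risk without guaranteeing an unexposed baseline.
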